Grant Writing	Prepare (Y4-Y5) [and submit (Y5)] an R01 application.				X	X
Responsible Conduct of Research	Biennial human subjects research re-certification through the Collaborative Institutional Training Initiative (CITI) (Y1, Y3, Y5)	X		X		X
	VCU- and department-wide ethics workshops and discussions with mentors and student scholars (Y1-Y5)	X	X	X	X	X
	CCTR 520: Fundamentals of Research Regulation - 2 hours/week in Y1. The regulations that govern translational and clinical research.	X				
	OVPR 601: Scientific Integrity - 1 hour/week in Y1. A survey of contemporary issues relating to responsible conduct in research.	X				
	OVPR 602: Responsible Scientific Conduct - 1 hour/week in Y2. A survey of issues relating to responsible conduct in research.		X			
	OVPR 603: Responsible Conduct of Research - 1 hour/week in Y2. This course will develop and refine skills needed to solve problems involving relevant topic areas of responsible scientific conduct.		X			
Workshops	Attend University of Washington Summer Institute in Statistical Genetics (3 weeks in Y1)	X				

## SPECIFIC AIMS

Aggressive behavior in the context of alcohol misuse is a substantial public health concern. Genetic predispositions have been identified for both aggression and alcohol misuse. However, the biological factors that predispose individuals towards alcohol-influenced aggression remain poorly understood. Specifically, the extent to which alcohol-influenced aggression is genetically-influenced is unknown. Further, it remains to be seen whether alcohol-influenced aggression is uniquely heritable, or is simply the by-product of genetic risk factors for both alcohol misuse and aggression. If alcohol-influenced aggression is found to be substantially genetically-influenced, the specific genetic and neural pathways through which these effects are transmitted must then be investigated. The goal of the research activities in this K01 proposal is to fill these gaps in our knowledge.

[figure not shown]
The overall objective of the research activities in this K01 award proposal is to examine the genetic factors and neural mechanisms that promote alcohol-influenced aggression. The proposed research activities will address the following research aims and test their associated hypotheses:

**Aim 1: Examine the extent to which genetic factors influence the extent to which individuals act aggressively in the context of alcohol misuse.** *Hypothesis 1:* Genome-wide complex trait analysis (GCTA) will reveal that alcohol-influenced aggression exhibits substantial genetic heritability.

**Aim 2: Examine whether genetic factors for alcohol-influenced aggression exist above-and-beyond genetic risk factors for general aggressiveness and alcohol misuse.** *Hypothesis 2:* After statistically controlling for genome-wide associations with non-alcohol-influenced aggression and alcohol misuse, significant genetic heritability will still be observed for alcohol-influenced aggression via GCTA.

**Aim 3: Identify the specific genetic loci and polymorphisms that are most strongly linked to alcohol-influenced aggression and create polygenic risk scores from these findings.** *Hypothesis 3:* Genome-wide association study (GWAS) techniques will identify specific gene polymorphisms associated with alcohol-influenced aggression.

**Aim 4: Identify functional and structural brain mechanisms that transmit the genetic effects on alcohol-influenced aggression.** *Hypothesis 4:* Polygenic risk scores for alcohol-influenced aggression will be associated with greater laboratory aggression, through changes in brain structure and function.

This proposal capitalizes on the resources available through [NIH-funded publicly-available datasets from the database of Genotypes and Phenotypes (dbGaP)] and VCU's Spit for Science (S4S) project, on which my primary mentor, [name] is a Principal Investigator. Drs. [name] and [name] (Co-Mentors) also play substantial roles in many of these projects. I would begin by analyzing existing data from [the dbGaP discovery sample], then seeking to replicate these findings with ongoing data collection for Spit for Science at my current institution, VCU. Finally, I would conduct a new MRI brain imaging study, using S4S participants (recruited based on their underlying genetic risk profiles) analyses in order to leverage my existing skillset in neuroimaging and laboratory aggression measurement and further accomplish the proposed research aims.

Accomplishing these aims would advance my long-term goal to become an independent alcohol investigator who integrates across multiple disciplines to study the factors that influence alcohol-influenced aggression. These activities would set the stage for R01-level applications to investigate the environmental factors that influence these effects, and biologically-informed interventions that might ameliorate them.

## RESEARCH STRATEGY

### A. Significance

A1. Aggressive behavior is a substantial public health concern in the United States, with approximately 1.2 million violent crimes occurring in 2015. Such violent crimes (e.g., aggravated assault, murder, rape) resulted in over 1.5 million non-fatal injuries and over 17,000 deaths in 2015. Previous estimates of these aggressive acts' financial toll was approximately \$177 billion. Violent crime is occurring with greater frequency in recent years, rendering the investigation and treatment of aggression an urgent issue. Alcohol is a significant factor in at least 40% of criminally violent acts. These frequency rates hold across juvenile and adult populations and soar to approximately 66% in the context of intimate partner violence. One in three college undergraduates experienced alcohol-influenced aggression and sexual assault rates on college campuses are drastically magnified by alcohol misuse. These statistics lead to the inevitable conclusion that alcohol-influenced aggression is a significant threat to public health and necessitates further research into its underlying bases.

A2. Alcohol is not merely correlated with greater aggression, but numerous laboratory experiments have shown that alcohol consumption causes increased aggression. Further, there exists a dose-response curve, in which greater doses of alcohol cause greater corresponding levels of aggressive behavior. Alcohol's ability to increase aggression is likely due to its ability to reduce inhibitory psychological processes and increase negative emotions such as anger and frustration.

A3. Despite alcohol's profound effect on aggression, there is substantial variability among individuals in the extent of the alcohol-aggression link. Indeed, not all alcohol misuse results in aggressive acts, yet the reasons for the underlying variability in this phenomenon remain incompletely understood. Given that variability in both aggression and alcohol misuse is substantially influenced by genetic components, it is likely that such heritable factors substantially contribute to individual differences in alcohol-influenced aggression.

A4. To date, there has been little-to-no investigation of the genetic basis of alcohol-influenced aggression. A substantial body of research has developed around the genetic basis of alcohol misuse and aggression, treating these outcomes separately. This has produced a critical gap in the understanding of aggression, alcohol consumption, and their interactive effects.

A5. Behavioral genetics should factor in the contextual nature of human behaviors. Attempts to identify the genetic basis of alcohol misuse and aggressive phenotypes are aided by modeling the complexity inherent in them. For instance, one study found that a genetic risk score for aggression's effect on intimate partner violence was moderated by a laboratory alcohol administration. Ignoring these contextual, environmental factors may underlie some of the irreproducibility of genetic associations with aggressive phenotypes. This project will model aggressive phenotypes alongside the contextual element of alcohol misuse, and use polygenic risk scores to predict such alcohol-induced aggression.

[figure not shown]
A6. Another beneficial development for genetic approaches to alcohol-influenced behaviors is the incorporation of neuroscientific approaches to test mechanistic hypotheses. Genetic effects on complex behaviors are likely mediated by changes in brain structure and function (see Figure 1 for conceptual model).

The added granularity provided by these neural mechanisms is critical for understanding how genetic influences impact outcome, and potentially for developing effective treatments for alcohol misuse. The proposed approach, which brings together polygenic, contextual, and neural mechanistic effects, is in line with the NIAAA Strategic Plan's goal to identify genomic and non-genomic mechanisms of alcohol effects.

### B. Innovation

The proposed research details a novel approach to understanding the biological basis of alcohol-influenced aggression. This project will advance the field in several ways. First, the genetic basis of alcohol misuse and aggression have been frequently investigated in separation, but rarely together. The proposed research will serve as the first systematic investigation of the genetic basis of alcohol-influenced aggression. Second, the proposed research will use existing data from the NIAAA-funded Collaborative Studies on Genetics of Alcoholism (COGA) project [*and four other publicly-available genomic datasets*] to develop novel polygenic risk scores for alcohol-influenced aggression. These risk scores would be a resource to the field and could be used by other researchers to examine this under-investigated behavioral phenotype. The proposed research will use these polygenic risk scores to identify at-risk individuals from another NIAAA-funded longitudinal project, *Spit for Science*. I will collect new data from these individuals using neuroimaging techniques and laboratory alcohol administration and aggression tasks. Building off of these ongoing projects is an efficient use of resources

Figure 1. Conceptual model through which genetic influences on alcohol-influenced aggression are mediated by functional and structural changes to the brain.

given the immense expense of longitudinal genotyping projects. Further, employing a sample of alcohol-dependent probands and a normative undergraduate sample will enhance the generalizability of the findings obtained in this research.

In addition to these innovative aspects, the research and training activities associated with this proposal will provide novel training for in genetic, genomic, and statistical methods, and conceptual knowledge of alcohol misuse phenotypes. I will combine this new skillset with my existing expertise in neuroimaging and aggression to begin a career of investigating alcohol misuse and its ability to magnify violence.

### C. Approach

The proposed research seeks to identify whether alcohol-influenced aggression has a substantially heritable genetic component (Aim I), that this heritability exists above-and-beyond genetic risk factors for general aggressiveness and alcohol misuse (Aim II), that specific genetic polymorphisms will be associated with alcohol-influenced aggression and these can be translated into polygenic risk scores (Aim III), and that these risk scores will exert their effects on alcohol-influenced aggression through specific alterations in brain function and structure (Aim IV). I will pursue these aims using [*a discovery sample comprised of five NIH-funded genomic datasets that are publicly available through the database of Genotypes and Phenotypes (dbGaP) and a replication sample from*] the NIAAA-funded VCU Spit for Science Student Survey.

#### Discovery Sample from dbGaP

The GWAS discovery sample ( $N = 31,123$ ) will be drawn from five ongoing and completed, multisite studies on the genetic basis of substance dependence and related behavior, available via dbGaP (Table 1).

**Table 1. List of dbGaP projects used in discovery sample ( $N = 31,123$ ).**

Project	Funding Source	Sample Size	Participants	dbGaP ID
Yale-Penn Alcohol Dependence GWAS (ADGWAS) 	NIAAA/NIDA	2,909	Alcohol-dependent participants + controls	phs000425.v1.p1
Collaborative Studies on Genetics of Alcoholism (COGA) 	NIAAA	17,783	Alcohol-dependent probands + genetic relatives, + controls	phs000092.v1.p1
Collaborative Genetic Study of Nicotine Dependence (COGEND) 	NCI	2,900	Nicotine-dependent probands + genetic siblings, + controls	phs000092.v1.p1
Family Study of Cocaine Dependence (FSCD) 	NIDA	1,044	Cocaine-dependent participants + controls	phs000092.v1.p1
Australian GWAS of Heroin Dependence (GWASHD) 	NIDA	6,487	Heroin-dependent participants + controls	phs000277.v1.p1

Participants. Across the discovery sample, participants exhibit substantial demographic variance (Table 2). The COGA sample, which is roughly generalizable to the other samples, exhibited substantial socioeconomic diversity (54.6% completed high school, median income: \$35,000, income range: \$1,000-150,000).

**Table 2. Demographics of dbGaP projects used in discovery sample.**

Project	Sex	Age Range	Age M(SD)	Ethnicity/Race
ADGWAS	46.9% F, 53.1% M	18-79	37.4 (11.8)	35.1% ED, 64.9% EM
COGA	53.7% F, 46.3% M	18-97	39.83 (14.6)	65.8% ED, 26.2% EM
COGEND	61.8% F, 38.2% M	25-47	36.5 (5.5)	55.4% ED, 44.6% EM
FSCD	50.3% F, 49.7% M	18-60	37.0 (8.8)	48.3% ED, 51.7% EM
GWASHD	47.0% F, 53.0% M	18-58	35.6 (9.2)	100% ED

ED=European-Descent, EM=Ethnic-Minority

Genotyping and imputation. Participants provided blood samples to biologic repositories, on which whole-genome genotyping was performed. Several genome-wide Illumina arrays were used, including the Human OmniExpress 12.VI, the Omni2.5 BeadChip, and the Human610-Quad BeadChip.] Genotypic data were checked for minor allele frequency (SNPs excluded with frequencies < 3%), pedigree structure/Mendelian inconsistencies, with samples imputed to 1000 Genomes using SHAPEIT and then IMPUTE2.

[figure not shown]
Phenotype measures. Participants completed the Semi-Structured Assessment for the Genetics of Alcoholism (SSAGA) [or variants of this instrument (e.g., Semi Structured Assessment for Drug Dependence and Alcoholism) that included our specific questions-of-interest]. The SSAGA includes reports of whether participants have previously performed physically-aggressive acts, and whether the acts were performed while participants had consumed alcohol or not (e.g., “have you ever physically injured anyone on purpose?”). Greater alcohol-influenced aggression is indicated by a greater number of yes (with alcohol) responses to such questions and non-alcohol-influenced aggression is indicated by a greater number of yes (no alcohol) responses. The SSAGA also assesses the extent to which participants have previously engaged in specific aspects of alcohol misuse (e.g., binge drinking).

#### Analytic Plan

Genome-wide complex trait analyses (GCTA). The initial analysis of the [discovery] dataset will seek to decompose phenotypic variance into the proportions that can be explained by genetic ( $h^2$ ) and

environmental/measurement-error factors. GCTA will quantify the heritability of aggressive, alcohol-misusing, and alcohol-aggressive phenotypes. GCTA will then be applied to determine the extent whether alcohol-influenced aggression has distinct heritability from general aggression and alcohol misuse (Figure 2A) or shares substantial genetic overlap with these two related phenotypes (Figure 2B).

**Figure 2. Competing conceptual models of the heritability of alcohol-influenced aggression.**

aggression, and alcohol misuse. Fixed-effects covariates will include age, ethnicity/race, sex, and socioeconomic status. To prevent heritability inflation, any two participants who share a second-cousin degree of relatedness or more will be excluded from subsequent analyses. A heritability ( $h^2$ ) estimate will be calculated for alcohol-influenced aggression, *controlling* for the heritability of non-alcohol-influenced aggression and alcohol misuse phenotypes. A substantial heritability estimate ( $h^2 > 0.1$ ,  $p < .05$ ) for alcohol-influenced aggression will serve as support for the unique genetic basis for this phenotype.

**Genome-wide association study (GWAS).** After the GCTA, GWAS will be used to identify single nucleotide polymorphisms (SNPs) and clusters of SNPs that are significantly associated with alcohol-influenced aggression. Due to the skewness of the alcohol-influenced aggression scores (see Figure 3), quasi-Poisson regression analyses will be used to accommodate such a distribution using the Bioconductor v2.1 package and SNPTEST v2.5. Specifically, alcohol-influenced aggression scores will be regressed onto principal components of the available SNPs using an additive model, excluding non-autosomal SNPs, with demographics factors as covariates. Due to racial stratification, separate GWAS will be performed for participants of African, American, East Asian, European, South Asian, and Mixed Race descent. Participants will be empirically assigned to these ancestral super-populations using the 1KGP population base and the Mahalanobis' distance between each population. I will meta-analyze these separate sets of GWAS findings METAL v3.0^32, which will produce meta-analytic '% variance explained' effect size estimates and  $p$  values for each SNP. [In addition to this meta-analytic approach, I will test for gene-by-race/ethnicity moderation using a kernel-machine approach to estimate whether each SNP's association with alcohol-influenced aggression varies across the discovery sample's diverse racial/ethnic groups, using the Robust Joint Tests package.] After correction for genetic inflation and weighting based on sample size, I will calculate polygenic risk scores for alcohol-influenced aggression [based on SNPs meeting increasingly stringent significance thresholds: .5, .4, .3, .2, .1, .05, .01, .001, .0001. The threshold that maximizes the variance explained ( $R^2$ ) in alcohol-related aggression will be used for risk score calculation.] Using an additive approach, I will sum across the number of alleles that are significantly linked to the phenotype, weighted by their respective effect size estimates from the GWAS. For example, if the A allele (versus the corresponding G allele) of a given SNP is significantly associated with greater alcohol-influenced aggression, then each copy of the A allele will be initially coded as +1 (GG = 0, GA = 1, AA = 2). These scores will then be multiplied by the GWAS effect size estimate for that given SNP. This polygenic risk scores will capture aggregate genetic risk for alcohol-influenced aggression in a manner that represents the current state of the field.

[figure not shown]

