#### **Feasibility**

Preliminary phenotypic analyses on the alcohol-influenced aggression scores from the COGA dataset, assessed among a subset of 9,273 participants, revealed a substantially-variable, albeit positively-skewed, distribution of alcohol-influenced aggression (Figure 3). Scores were distributed across the possible 0-10 range of the score, median = 1.00,  $M = 1.57$ ,  $SD = 1.73$ . These initial estimates of phenotypic frequencies suggest that there will be sufficient proportions of participants to adequately power the analyses in this proposal.

**Power analysis.** Power calculations for the GCTA heritability analysis, which assumed an underlying

These analyses will be conducted with the GCTA software toolkit v1.26, using a restricted maximum likelihood method to compute a bivariate genetic relationship matrix by correlating the genetic similarity between each participant. Then, these genetic similarity estimates are modeled as random effects predictors of each phenotype: alcohol-influenced aggression, non-alcohol-influenced

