**Figure 3. Frequencies of a subset of COGA participants' alcohol-influenced aggression scores.**

heritability of  $h^2 = 0.2$ , a type I error rate of 0.05, and a variance of SNP-derived genetic relationships of .00002, suggested that 80% power for the proposed GCTA can be obtained with 4,430 participants. The [discovery] sample far exceeds this sample size at over [31,000] participants. GWAS power analyses, implemented via the GWAS.PC v1.0 package for R statistical software were also performed to determine the minimum effect size (in units of % variance explained) that [the discovery sample could detect with 80% power. Calculations were based on the planned detection of multiple, additive SNP markers, an alpha level of .05, and a minor allele frequency of 0.05, revealing that the proposed GWAS is able to detect effect sizes of 0.09% variance-explained and larger. However, this is likely an optimistic assessment as this power analysis did not account for the moderating effects of ethnicity/race and the genetic relatedness of participants (yet recent research has indicated that GWAS power is not significantly affected by underlying genetic relationships between participants).]

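### GCTA controls for ancestry only through a race covariate and for study not at all, so structure can inflate h² and could falsely meet the Aim 2 support rule

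*Combined protocol and SAP*

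**What the plan says.** The discovery-sample Analytic Plan opens with GCTA: "The initial analysis of the [discovery] dataset will seek to decompose phenotypic variance". REML is used to "compute a bivariate genetic relationship matrix by correlating the genetic similarity between each participant" (this sentence is displaced into the Feasibility text by the PDF extraction). On adjustment, the plan says: "Fixed-effects covariates will include age, ethnicity/race, sex, and socioeconomic status". The only stated guard against inflation is to exclude "any two participants who share a second-cousin degree of relatedness or more".

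The support rule, h² above 0.1 with p below .05, is attached to the estimate for alcohol-influenced aggression that controls for non-alcohol aggression and alcohol misuse. That is Aim 2. Aim 1, in Specific Aims, predicts substantial heritability but sets no threshold.

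The power paragraph derives a requirement of 4,430 participants and notes that the "sample far exceeds this sample size at over [31,000] participants".

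The GWAS paragraph treats ancestry differently: "Due to racial stratification, separate GWAS will be performed for participants of African, American, East Asian, European, South Asian, and Mixed Race descent". Empirical ancestry assignment, SNP principal components and an inflation correction appear there and are not carried back to GCTA.

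**The concern.** GCTA attributes to genes any phenotypic similarity that tracks genome-wide similarity. In a mixed sample, genome-wide similarity also tracks ancestry and, through recruitment, study. A race covariate removes mean differences between race categories. It does not remove admixture within a category or differences between studies of the same category.

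The discovery sample is exposed to both. By Tables 1 and 2 the five studies range from 0% to 64.9% minority. They were ascertained on alcohol, nicotine, cocaine or heroin dependence, one is Australian, several arrays were used, and some studies used variants of the interview. Differences between studies in alcohol-influenced aggression are therefore plausible. With the COGA SD of 1.73, a shift of 0.3–0.5 SD is 0.3 × 1.73 = 0.5 to 0.5 × 1.73 = 0.9 points on the 0–10 score.

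At stake are the Aim 1 heritability estimate and the claim in Aim 2 that alcohol-influenced aggression has a genetic basis of its own.

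**Working it through.** **The plan's own figure.** Inputs from the power paragraph: h² = 0.2, alpha 0.05, 80% power, variance of genetic relationships 0.00002.

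SE(h²) = √(2 / 0.00002) / N = 316.23 / N

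N = (1.960 + 0.842) × 316.23 / 0.2 = 4,430 (two-sided). The plan's figure reproduces; a one-sided test would give 3,931.

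**What p < .05 protects against.** At N = 31,123, SE = 316.23 / 31,123 = 0.010. Any estimate above 1.96 × 0.010 ≈ 0.02 is significant, so the 0.1 cut-off does the deciding.

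**Sample make-up (Tables 1 and 2).**
- European descent: 1,021 (ADGWAS) + 11,701 (COGA) + 1,607 (COGEND) + 504 (FSCD) + 6,487 (GWASHD) ≈ 21,320.
- Minority: about 8,380. The COGA shares sum to 92%, so the two totals fall short of 31,123.
- GWASHD is 6,487 / 21,320 = 30% of the European-descent total. The race covariate cannot absorb a GWASHD difference.

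**Null simulation (true h² = 0).** Study sizes and ancestry shares follow Tables 1 and 2, with the COGA shares rescaled. About 52,000 independent SNPs were used, so that the relationship variance within European descent is close to the plan's 0.00002. Inference was by REML with a half-chi-square likelihood-ratio test, with 200 replicates at N = 4,430 and 100 at N = 10,000. Study shifts, drift, the admixture distribution, a single two-way admixed minority group and a Gaussian phenotype are assumptions.

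Share of runs with h² > 0.1 and p < .05, pooled sample, race as the only structure covariate:

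| Scenario | N = 4,430 | N = 10,000 |
|---|---|---|
| No structure effect | 8% | 0% |
| GWASHD shifted 0.2 SD | 16% | 1% |
| GWASHD shifted 0.3 SD | 42% | 17% |
| GWASHD shifted 0.5 SD | 94% | 97% |
| Gradient on minority admixture, 1% of variance | 93% | 78% |
| Gradient on a European cline, 1% of variance | 57% | 34% |
| Any of these, with study terms and 10 PCs | 4–8% | 0–1% |

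Monte Carlo error is modest: √(0.42 × 0.58 / 200) = 3.5 points for the 42%, and √(0.17 × 0.83 / 100) = 3.8 points for the 17%.

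Splitting by ancestry is not enough by itself. In European-descent participants only (N about 3,160), with no study or PC term, the rule was met in 56% of runs at 0.3 SD and 100% at 0.5 SD.

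**Full N.** A one-axis likelihood calculation at N = 31,123, with drift F from 0.0005 to 0.005, gives these spurious h² values, all with p < .05:
- 0.2 SD shift: 0.04–0.05
- 0.3 SD shift: 0.055–0.076
- 0.5 SD shift: 0.08–0.125

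**Which N applies.** Table 1 says COGA and COGEND include relatives, so exclusions will reduce N. Dropping both entirely leaves 2,909 + 1,044 + 6,487 = 10,440, so results near N = 10,000 are relevant.

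**Relationship variance.** The simulated European-descent value was 0.0000198, which matches the plan's input. The simulated pooled matrix gave about 0.0012. The power calculation therefore describes a homogeneous group, not a pooled one.

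**The case against.** Several points on the other side stand.

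- The plan never calls GCTA pooled, and a list of what covariates will include is not strictly closed. Pooling is an inference from the analysis of the whole discovery set, the single relationship matrix and the comparison with 31,000. No GCTA split or further covariate is described anywhere.
- A reader might infer that both Aims stand or fall on the 0.1 threshold. The text ties it only to the conditional Aim 2 estimate. The simulations use a single phenotype and do not model that estimate. Conditioning on aggression and misuse might absorb part of any shared structure, so the false-pass rate of the planned Aim 2 test has not been shown.
- A reader might infer that a false pass is likely whatever the circumstances. It is not. Most rates fall as N rises, and at full N a single axis shifted by 0.3 SD or less usually stays below 0.1. Crossing it needs about 0.5 SD with low drift, or an admixture gradient. Several axes acting together were not simulated.
- A reader might infer that the relatedness filter will remove unrelated minority participants. That depends on how relatedness is measured, which the plan does not say; pedigree structure was checked at genotyping. Only if a cut-off such as 0.025 (assumed) were applied to the pooled matrix would it happen: 98–99% of simulated minority pairs exceeded that value. The filter does not cure the bias either: no simulated European-descent pair exceeded 0.025, yet the inflation remained.
- GCTA gates nothing. The GWAS follows regardless of the h² result, the fallback risk score is triggered by the GWAS, and MRI recruitment uses scores from the discovery GWAS.

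**Conclusion.** The concern holds as a risk of bias. Followed as written, GCTA leaves ancestry structure within race categories and differences between studies free to enter h². That can inflate the Aim 1 estimate and could falsely meet the Aim 2 rule. The risk ranges from small (a 0.2 SD shift at N = 10,000) to near certain (0.5 SD), and adding study terms and PCs restores about the nominal rate or lower. At full N, the more likely harm from one modest axis is a highly significant but spurious h² below 0.1.

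These sizes rest on assumed shifts, drift and gradients that the documents do not give, and on a single Gaussian phenotype. The omission itself does not depend on them. The plan recognises stratification for the GWAS and does not carry that protection to GCTA. It should be fixed before analysis, but a false h² would mislead the reporting of Aims 1 and 2 without altering the conduct of Aims 3 and 4.

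**What to change.** State in the GCTA section that:

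1. GCTA is run within each ancestry group large enough to estimate h², using the empirical assignment already planned for the GWAS.
2. The relationship matrix is built, and the relatedness cut-off applied, within group, with the measure of relatedness and the numerical cut-off stated.
3. Ancestry PCs and study/array indicators are added as fixed effects in every group.
4. Group estimates are combined by inverse-variance weighting, and the h² > 0.1 rule is applied to the combined conditional Aim 2 estimate.

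The change costs analysis-plan wording, a few extra runs and larger standard errors; it needs no new data. On the plan's own formula, take the unfavourable case in which COGA and COGEND are dropped entirely (N = 10,440):

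- Unsplit: SE = 316.23 / 10,440 = 0.0303; power at h² = 0.1 is Φ(0.1 / 0.0303 − 1.96) = 91%. This figure must not be used to cost the fix, because it ignores the split.
- Split into European descent (1,021 + 504 + 6,487 = 8,012; SE 0.0395) and minority (1,888 + 540 = 2,428; SE 0.130): combined SE = 1 / √(1/0.0395² + 1/0.130²) ≈ 0.0378. Power is Φ(0.1 / 0.0378 − 1.96) ≈ 75% at h² = 0.1, and over 99% at the planned h² = 0.2.

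Dividing the minority group further lowers power somewhat, and very small ancestry groups may not be estimable; the plan should say how they are handled. If European-descent COGA participants were all retained (about 21,320 before exclusions), power would exceed 99% at either value, but relatives must be removed first.

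### The relatedness exclusion as worded drops both members of a related pair, does not say whether it covers the GWAS, and is not reflected in the stated sample sizes

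*Combined protocol and SAP*

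**What the plan says.** All references are to the combined protocol and SAP.

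- **Analytic Plan, GCTA text around Figure 2.** The exclusion is introduced with the purpose "To prevent heritability inflation" and states that "any two participants who share a second-cousin degree of relatedness or more will be excluded from subsequent analyses". It has no provision to keep one member of a pair and does not name the analyses it covers.
- **Analytic Plan, GWAS paragraph.** "After the GCTA, GWAS will be used to identify single nucleotide polymorphisms". The model is a quasi-Poisson regression with principal components of the SNPs and demographic covariates. No kinship or family term is described. A correction for genetic inflation is applied before risk scores are calculated.
- **Table 1.** The discovery sample is 31,123. COGA (17,783) is described as "Alcohol-dependent probands + genetic relatives, + controls" and COGEND (2,900) as "Nicotine-dependent probands + genetic siblings, + controls".
- **Feasibility, Power analysis.** The GCTA needs 4,430 participants for 80% power, and the discovery "sample far exceeds this sample size at over [31,000] participants". The GWAS is said to detect 0.09% of variance explained with 80% power at an alpha of .05. The text adds that this calculation "did not account for the moderating effects of ethnicity/race and the genetic relatedness of participants", and then cites research that relatedness has little effect on GWAS power.

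No sample size after exclusion appears anywhere.

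**The concern.** Two thirds of the discovery sample comes from studies that recruited relatives, so a relatedness exclusion is not a marginal rule here. The wording leaves two questions open: whether one or both members of a pair are removed, and whether the GWAS is one of the later analyses.

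Either answer to the second question leaves a gap. If the rule covers the GWAS, the detectable effect given for the discovery sample rests on people who will not be analysed. If it does not, relatives enter the GWAS as independent observations. Removing both members also discards people who could be kept without leaving any related pair in the data.

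The GWAS results feed the polygenic score. The fallback to a product of external scores depends on whether any SNP is significant. The discovery score is also used to select the 202 imaging participants. Who is in the GWAS, and how relatedness is handled, should therefore be settled beforehand.

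**Working it through.** **Inputs.** Study sizes come from Table 1. From the Power analysis: h² = 0.2, alpha .05, variance of genetic relationships .00002, 80% power, and a GWAS detectable effect of 0.09%. The share of participants with a relative in the data is not given, so it is varied.

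**1. Share of the sample.** 2,909 + 17,783 + 2,900 + 1,044 + 6,487 = 31,123. COGA plus COGEND = 20,683, and 20,683 / 31,123 = 66.5%. The other three studies total 10,440. This is the lowest N if losses are confined to the two studies that Table 1 describes as including relatives or siblings. Both also include controls, so it is an extreme case.

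**2. The plan's GCTA figure.** With SE(h²) = √(2 / (N² × var)), required N = (1.960 + 0.842) × √(2 / .00002) / 0.2 = 4,429.7. The stated 4,430 reproduces (two-sided).

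**3. GCTA at reduced N.** At N = 10,440, power for h² = 0.2 is above 99.9%. For h² = 0.1, the plan's own threshold for substantial heritability, the required N is 8,860 and power at 10,440 is 91%.

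**4. The plan's GWAS figure.** For a 1-df test, the non-centrality is N × q² / (1 − q²), where q² is the proportion of variance explained. At two-sided alpha .05 and 80% power it must equal (1.960 + 0.842)² ≈ 7.85.
- N = 31,123: q² ≈ 7.85 / 31,123 = 0.025%.
- N = 10,440: q² ≈ 7.85 / 10,440 = 0.075%.

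The stated 0.09% does not reproduce. Worked backwards, 31,123 × .0009 / .9991 = 28.04, whose square root is 5.295. Subtracting 0.842 leaves a critical value of 4.453, a two-sided alpha of about 8.5e-6.

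**5. Scaling the stated 0.09% by 1/N.** This is conditional on that implied alpha, on 31,123 having been the N used, and on an assumed share lost.

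| Share of COGA + COGEND lost | N | Detectable effect | Power for 0.09% |
|---|---|---|---|
| 0% | 31,123 | 0.09% | 80% |
| 25% | 25,952 | 0.108% | 65% |
| 50% | 20,782 | 0.135% | 45% |
| 75% | 15,611 | 0.179% | 24% |
| 100% | 10,440 | 0.268% | 8% |

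**6. One member or both.** As an illustration, suppose all 20,683 were in families of three mutually related members. Keeping one per family gives 10,440 + 20,683 / 3 = 17,334, against 10,440 when all related members are removed.

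**The case against.** The strongest reply concerns scope. The rule sits in the GCTA text, its stated purpose is specific to heritability estimation, and a heritability estimate follows directly. A GCTA-only reading is plausible, and the GWAS power text, which discusses relatedness as a live feature of the data, fits it. The wording about pairs may also be a loose way of saying one per pair. Both points stand. A reader might infer that the plan definitely removes both members from every later analysis, the GWAS included, but the documents do not settle that. Under the GCTA-only reading, however, the GWAS has relatives and no term for them, and the GCTA number is still overstated.

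A second reply is that the GCTA claim of adequacy survives. It does: 10,440 is about 2.4 times 4,430. The documents do not support an inference that the GCTA is underpowered for h² = 0.2.

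Third, a reader might infer that exclusion alone makes 0.09% unattainable. At the stated alpha of .05 it does not, since even 10,440 participants detect about 0.075%. The larger figures in the table need an alpha that the plan does not state.

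Fourth, the plan applies a correction for genetic inflation, calls its GWAS power estimate optimistic, and concedes that the datasets are underpowered. The correction is a partial remedy for inflated test statistics. It does not say who is analysed and does not model family structure. The optimism is attributed to unmodelled relatedness and ancestry, not to lost participants, and the relatedness part is then discounted.

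**Conclusion.** The point holds as a gap in specification with a numerical consequence. As worded, the rule removes both members of each related pair and leaves its scope open. The GCTA sample will be below the stated figure by an unknown amount, no lower than 10,440 if losses are confined to COGA and COGEND. The conclusion that the GCTA is large enough is unaffected.

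For the GWAS, if the rule applies, the N behind the detectable effect is too large. If it does not, standard errors are likely too small, with only partial protection from the inflation correction. How much too small cannot be computed, because family sizes and within-family correlation are not given.

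The range of 0.11% to 0.27% for 25% to 100% loss is illustrative only, for the reasons given with the table. No effect on the imaging study has been quantified, and none should be inferred from the single-SNP detectable effect: the score uses thresholds from .5 to .0001, and recruitment is from the extremes of the score.

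**What to change.** 1. **GCTA.** State that one member of each pair related at second-cousin level or closer is removed, chosen to retain the most participants. Restate the GCTA N after exclusion.
2. **GWAS.** Say which approach is used: the same unrelated set, or all participants with a kinship random effect or family-clustered variance.
3. **Power.** Recompute the GWAS detectable effect at the resulting N and at the alpha actually used, and state that alpha, since 0.09% does not correspond to .05.

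The cost is rewording, a relatedness count in the discovery data and one recalculation. Keeping relatives would also need a model or variance estimator that handles them. The downside is a less favourable stated N and possibly a less favourable detectable effect.
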